#### 4) Inclusion and Exclusion Criteria

Inclusion criteria: A subject will be eligible for study participation if subject meets all following criteria:

- 1. Subject has Fragile X syndrome with a molecular genetic confirmation of the full FMR1 mutation (>200 CGG repeats) or the other loss of function mutations of the FMR1 gene (SNVs and deletions of the gene).
- 2. Subject is a male or non-pregnant, non-lactating female age 6 through 35 years, inclusive.
- 3. Subjects who are capable of becoming pregnant must use an acceptable method of birth control for the duration of the study. Acceptable forms of birth control include abstinence (only for subjects who are not sexually active), intrauterine devices in place for at least 3 months, oral contraceptives, surgical sterilization, or adequate barrier methods.
- 4. Subject must have a caregiver (parent, guardian, or other legally authorized representative) who is willing to participate in the whole study.
- 5. Subject and caregiver are able to attend the clinic regularly and reliably.
- 6. Subject and/or subject's caregiver is able to understand, read, write and speak English or French fluently to complete study-related materials.
- 7. For subjects who are not their own legal guardian, subject's caregiver is able to understand and sign an informed consent to participate in the study.
- 8. The use of concomitant medication must be stable, in terms of dose and dosing regimen, for at least 4 weeks prior to Screening and must remain stable during the period between first visit (Screening) and the commencement of the study; every effort should be made to maintain stable regimens of allowed concomitant medications from the time of commencement of double-blind study medication until the last study assessment.
- 9. Behavioral/educational treatments must be stable for 4 weeks prior to first visit (Screening) and must remain stable during the period between Screening and the commencement of randomized double-blind study medication.

10. Overall age equivalent is not higher than 13 and IQ is not higher than 85, as assessed at Screening on the Leiter-III, and subject must speak at least occasional 3-word phrases.

#### Exclusion criteria:

- 1. Families that are not cooperative and will not follow through with the demands of this study.
- 2. Subject has a life-threatening medical problem or other major systemic illness that compromises health or safety and/or would interfere with this study.
- 3. Age younger than 6 or older than 35 years.
- 4. History of intolerable adverse events with metformin.
- 5. Current or recent metformin treatment (within the past 4-months).
- 6. BMI inferior to 2 standard deviations below the mean for age using the World Health Organization scale.
- 7. Serum creatinine > 1.4 mg/dl (female) or > 1.5 mg/dl (male).
- 8. History of metabolic acidosis or a condition with lactic acidosis.
- 9. Severe Vitamin B12 deficiency.
- 10. Pregnancy at screening or unwillingness to use acceptable method of birth control, if applicable.
- 11. Age equivalent higher than 13 or IQ higher than 85 on the Leiter-III at Screening.

No additional inclusion criteria will be assessed for the extension phase. Participants can choose to enter the extension phase after successfully completing the main study (randomized controlled trial - RCT). A washout between the RCT and extension phase will not be required.

Inclusion criteria for the controls providing a stool sample:

- 1. Able to provide a stool sample
- 2. Able to read and write in English in order to complete a questionnaire (or have a parent/caregiver able to do this)
- 3. Age 6-35 years old

Exclusion criteria for the controls providing a stool sample:

- 1. Diagnosis of Fragile X Syndrome
- 2. Unable to provide a stool sample
- 3. Younger than 6 or older than 35 years old
- 4. Metformin Treatment within the past 4 months

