### 7) Procedures Involved

At the first visit, baseline testing will include IQ testing with the Leiter-III and assessment for autism with the Autism Diagnostic Observation Scale (ADOS-2). Cognitive ability will be derived from the Leiter-III, only at baseline. We have shown that full mutation males often perform at the floor of standardized intelligence tests, such as the Wechsler Scales of intelligence, which severely restricts test sensitivity and variability, and therefore presents major limitations in analyses examining genotype-phenotype associations. The primary reason that we have chosen the Leiter-III is because it is a non-verbal test, and it can be used even with low-functioning patients who have little or no language. The ADOS-2 (Lord et al., 2000) is a semi-structured standardized assessment administered directly for the purposes of diagnosing ASD, and will be done only at baseline. The ADOS-2 uses developmentally appropriate social and object-based interactions in a 30–45 minute assessment to elicit symptoms of ASD in four areas: social interaction, communication, play, and repetitive, restrictive behaviors. The ADOS-2 consists of different modules, each directed at a particular level of language ability, and is thus appropriate to use across subjects of varying ages and functioning levels.

The CGI-S, VAS, ABC-C, ADAMS, CSHQ, SNAP-IV, PedsQL, EQ-5D, CarerQoL, Sensory Profile-2 or Sensory Profile Adolescents/Adults, ASA24, and the memory game will be completed.

Blood will also be drawn for safety laboratory tests, including a hemoglobin A1c (HgbA1c), blood glucose, complete blood count (CBC), vitamin B12 level, comprehensive metabolic panel (CMP), cholesterol, renal clearance function, blood pregnancy test for female participants in childbearing age, along with biomarker studies described below. A small skin biopsy (optional procedure) will be obtained from the back of the shoulder, utilizing a small punch biopsy after numbing the skin with lidocaine or EMLA cream, so that fibroblasts can be grown on each patient at baseline to determine the level of Fragile X Mental Retardation Protein (FMRP), the presence of tissue mosaicism, and other studies described below. At the first visit, a detailed medical history and physical and neurological examination will be carried out, with all medications and medical problems documented. A urine and stool sample will also be collected.

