Patients will be randomized to either metformin or placebo by the Alberta Health Services Pharmacy Research Office and by the Service pharmaceutique de support à la recherche (SPSR) of CHU Sainte-Justine (University of Montreal) for their participants after the baseline studies are carried out, as detailed below. For patients 50 kg and over, the initial dose will be 500 mg once a day at dinner by mouth, and then increasing each week by 500 mg until a maximum dose of 2000 mg daily is reached. For those patients who are less than 50 kg, the initial dose will be 250 mg once a day at dinner by mouth, and if this dose is well tolerated, they will increase each week by 250 mg until a maximum dose of 1000 mg daily is reached. As such, the maximum dose of metformin in patients under 50 kg will be 1000 mg daily. We will recommend all patients to take a multiple vitamin that has B12 to avoid potential anemia. In the first 4 weeks following visit 1, each patient will receive a weekly call to evaluate tolerability of the medication, any adverse events (AEs), changes in concomitant medications, and gradual titration of the metformin. If potentially related minor AEs such as diarrhea or gastrointestinal pain are experienced, the dose can be lowered, or medication held until clinically indicated to resume the trial.

At 2 months (Week 8 +/- 7 days, scheduled visit 2), when at their maximum tolerated dose, they will be seen in clinic for an examination, fasting safety labs (consisting of the lipid panel which includes cholesterol, LDL, and triglycerides; complete blood count; and comprehensive metabolic panel), urine, biomarkers, assessment of AEs, and limited studies, including a CGI-I, VAS, and behavioral and quality of life questionnaires (ABC-C, ADAMS, CSHQ, SNAP-IV, PedsQL, EQ-5D, Sensory Profile-2 or Sensory Profile Adolescents/Adults, and CarerQoL). We will require 8 hours of fasting prior to the visit 2 blood draw. Participants will only be allowed water during the fasting period.

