Subjects will remain at the designated dose through Visit 3 (at Week 16/end of treatment +/-7 days) and will be contacted at week12 by study staff via phone to assess for possible adverse events, changes in concomitant medications, and verification of proper dosing. Study participants will be dispensed study medication at Visits 1 and 2 and will discontinue dosing after completing Visit 3. Any change in medication or new medication will also be documented. The examination, safety labs, biomarkers, urine and stool collection, documentation of AEs, and outcome measures will be repeated at the final follow-up visit at 4 months/end of treatment. We will also record any seizure activity that occurs throughout the study using a seizure diary (which the participant/caregiver will take home) where the date, time, seizure type, duration, whether the participant was awake or asleep during the seizure, use of baseline and abortive medication, as well as any changes to medication. We will also suggest to families to attempt to video record the episodes when possible (on a phone or other camera). They will be asked to show the study doctor or their primary care physician the video as part of standard of care for patients. We will not retain a copy of the video.

Remote visits may be utilized for visit 2 if deemed appropriate by the PI. It will save on travel cost and burden to families. When this is the case, the urine dipstick and research blood work will not be performed. Questionnaires will be sent to the family and the physical exam will be performed virtually via tele/videoconference, for example via Zoom. Study medication will be mailed to participants.

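### The only renal exclusion is a creatinine limit that ignores age and body size, so it is loosest in the smallest children and can pass unrecognised moderate impairment

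*Combined protocol and SAP*

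**What the plan says.** Section 4, exclusion 7, excludes on "Serum creatinine > 1.4 mg/dl (female) or > 1.5 mg/dl (male". None of the other criteria (10 inclusion, 11 exclusion in all) names a renal measure, and the same two values apply from age 6 through 35.

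The protocol does adjust for age or size elsewhere. Exclusion 6 uses "BMI inferior to 2 standard deviations below the mean for age using the World Health Organization scale". Section 7 sets dose by weight: "the maximum dose of metformin in patients under 50 kg will be 1000 mg daily".

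Other text bears on renal safety:

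- Exclusion 2: "Subject has a life-threatening medical problem or other major systemic illness that compromises health or safety". This is a judgement and names no test.
- Section 7, baseline bloods: "comprehensive metabolic panel (CMP), cholesterol, renal clearance function, blood pregnancy test for female participants in childbearing age". No method, threshold or eligibility consequence is attached to the clearance item, and the detailed laboratory table lists BUN and creatinine but no eGFR or clearance.
- Section 12 describes lactic acidosis as rare when renal function is sound, and counts on the safety labs to screen out people at risk of it.
- Section 7 has the pharmacies randomise "for their participants after the baseline studies are carried out, as detailed below", and then: "Study participants will be dispensed study medication at Visits 1 and 2 and will discontinue dosing after completing Visit 3". Nothing says that the creatinine result must be in hand before the first dose.
- For the extension, Section 4 says "No additional inclusion criteria will be assessed for the extension phase". A footnote to the schedule in Section 7 carries forward the criteria met at the start of the RCT.

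**The concern.** Serum creatinine reflects body size as well as kidney function. A limit that is reasonable for a tall adolescent therefore corresponds to a lower level of renal function in a six-year-old. A small child whose moderate impairment has never been recognised can have a creatinine well below 1.4 or 1.5 mg/dl and be enrolled under the rule exactly as written.

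This matters because the protocol itself ties the drug's most serious listed reaction to renal insufficiency. Exclusion 7 is the one place where a renal laboratory value becomes an entry decision. The exposure may also be long: up to two further years in the extension, with no renal rule applied on entry.

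**Working it through.** The protocol states no eGFR figure, so there is nothing of its own to reproduce.

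**Inputs from the protocol:** cut-offs of 1.4 mg/dl (female) and 1.5 mg/dl (male); ages 6 to 35.

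**Assumptions, not in the protocol:** eGFR = k × height (cm) / creatinine (mg/dl), with k from 0.413 to 0.55; height of 105 to 125 cm at about age 6; moderate impairment means eGFR 30 to 59 mL/min/1.73 m².

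**Step 1: eGFR of a child exactly at the limit.** For example, a girl of 105 cm: 0.413 × 105 / 1.4 = 31.0.

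| Height | Girls, k 0.413 | Girls, k 0.55 | Boys, k 0.413 | Boys, k 0.55 |
|---|---|---|---|---|
| 105 cm | 31.0 | 41.3 | 28.9 | 38.5 |
| 125 cm | 36.9 | 49.1 | 34.4 | 45.8 |
| 140 cm | 41.3 | 55.0 | 38.5 | 51.3 |
| 170 cm | 50.2 | 66.8 | 46.8 | 62.3 |

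Every value at 105 to 125 cm is below 60. Widening k down to 0.35 gives 26.2 to 31.3 in girls and 24.5 to 29.2 in boys at those heights, so the conclusion does not depend on the lower end chosen for k.

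**Step 2: the gap by height.** At a fixed creatinine and a single k, eGFR is proportional to height, so k cancels. Relative to a 170 cm participant of the same sex:

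- 105 cm: 1 − 105/170 = 38% lower
- 125 cm: 1 − 125/170 = 26% lower
- 140 cm: 1 − 140/170 = 18% lower

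**Step 3: what the rule lets through.** Creatinine at eGFR 60 is k × height / 60:

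- 0.413 × 105 / 60 = 0.72 mg/dl
- 0.413 × 125 / 60 = 0.86 mg/dl
- 0.55 × 105 / 60 = 0.96 mg/dl
- 0.55 × 125 / 60 = 1.15 mg/dl

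The range 0.72 to 1.15 mg/dl is 52% to 82% of the girls' limit (0.723/1.4 and 1.146/1.4) and 48% to 76% of the boys' (0.723/1.5 and 1.146/1.5). A child of 105 to 125 cm at the upper edge of moderate impairment is not close to exclusion.

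**Step 4: whether another provision closes the gap.** The baseline clearance item has no threshold. Urinalysis depends on the participant giving a sample. Exclusion 2 and the medical history depend on disease already being recognised. Section 10 asks for laboratory abnormalities to be assessed and reported, not for exclusion. At extension entry, Visit 3 or first-visit labs are available, but no renal rule is applied to them. None of these obliges exclusion.

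**The case against.** The strongest reply is about weight. The protocol contains no eGFR equation, no participant heights and no renal level at which metformin becomes unsafe, so the size of the effect comes from outside assumptions. That is true, and it is why ranges are given.

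The comparison by height also applies a paediatric formula to a 170 cm participant who may be an adult. Under an adult creatinine equation (CKD-EPI 2021, again an assumption), people aged 18 to 35 at the limit have about 50 to 56 (women) and 62 to 69 (men). At k = 0.55 a girl of 125 cm is at 49, so the gap to adult women almost disappears, and at 140 cm (55) it is no longer visible. For small girls the size of the gap therefore depends on k. For boys it is clear throughout. Different equations are not strictly comparable, and adult women passing at 50 to 56 would mean that the weakness is worst in small children but not confined to them.

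Renal screening is not absent either. There are the clearance item, baseline and on-study lactate, metabolic panels, weekly calls during titration, half the maximum dose below 50 kg, advice to stop for symptoms of lactic acidosis, and unblinded DSMB review twice a year. Extension entrants have on-study labs, and safety labs are repeated at 1 and 2 years. A careful investigator may well catch a case. Nothing in the protocol suggests that renal disease is frequent in this population.

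These points lower the likely harm. They do not supply the missing threshold, and at 105 to 125 cm they do not reverse the direction.

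**Conclusion.** The concern holds, as a point that should be fixed rather than one that threatens the trial. The text is unambiguous: one renal criterion, set by sex only, from age 6 through 35. On the stated assumptions, a child of 105 to 125 cm can pass with an eGFR of about 31 to 49 (girls) or 29 to 46 (boys). The lowest boys' value falls just below the moderate band. The problem narrows as height increases.

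The gap concerns impairment that nobody has yet recognised. The documents give no basis for estimating how many children that is, and the mitigating measures are real. Power and type I error are unaffected. Confidence is medium, because the size rests on an outside formula while the direction at these heights does not depend on the value of k.

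**What to change.** Add to exclusion 7 that participants under 18 are also excluded if serum creatinine exceeds the local laboratory's upper limit of normal for age and sex. Alternatively, exclude below a height-based eGFR threshold chosen by the clinical team, calculated from the baseline creatinine and the height already needed for exclusion 6. The first option is simpler but stricter than screening for moderate impairment; the second is closer to the target.

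State that this check is what the baseline renal clearance item means, and require the result before the first dose. At extension entry, apply the same check to the RCT Visit 3 labs, or to the extension first-visit labs for those entering more than a year later.

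The cost is a short amendment, possibly a few more screen failures, and a wait for the result before dosing. No extra blood test is needed, because creatinine is in the metabolic panel. Two limits remain: the rule steps at age 18, and Visit 3 labs may be up to a year old at extension entry. Even so, the plan would be safer than it is now.

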#### **Consenting Process:**

Subjects will be recruited and consented at each site. The research coordinator will speak with both the subject and at least one caregiver to explain the research and associated study procedures and assess the subject's understanding of the protocol. Subjects aged 6 will not provide

Page 7 of 47

1 November 2022

Pro00081059

assent; consent will be obtained from the caregiver (Caregiver (Parent/ Legal Guardian) Consenting for Participants Information & Consent Form). For all subjects 7-35, cognitive ability will be assessed utilizing the Capacity Assessment Checklist for Informed Consent with Cognitively Impaired Subjects, also used at the MIND. Study coordinators will perform the initial capacity assessment, which will be reviewed with the study doctor before any other study procedures are done and signed by the study doctor. If appropriate based on cognitive age and ability, assent will be obtained from subjects aged 7-17; if the assent form is not appropriate for the subject's cognitive age and ability, study staff will instead provide a letter of information that will be read to and reviewed with the subject. In the event of changes to the protocol that could possibly affect subjects' safety or decision to participate in the study, current subjects and/or their caregiver will be informed of the changes and re-consented for continuing participation in the study.

In addition to the assenting process described above, all subjects under the age of 18 will need to have their caregiver sign the consent form. Subjects 18 and older who are cognitively capable of providing consent (based on the Capacity Assessment Checklist for Informed Consent with Cognitively Impaired Subjects mentioned previously) will sign an informed consent form (Adult Participants and Caregiver Information and Consent). For subjects 18 or older at screening/baseline, or for those who turn 18 during the course of study participation, who are not cognitively capable of providing consent, a caregiver will need to sign the consent form used for subject with parents consenting (Caregiver (Parent/ Legal Guardian) Consenting for Participants Information & Consent Form). All potential subjects will attend their screening visit with a caregiver able to give surrogate consent.

Separate consent forms (at University of Alberta) or separate signatures (at CHU Sainte-Justine) for either subject or caregiverwill be filled or obtained for the optional biobanking of blood,urine (cell culture), and stool as well as for the optional skin biopsy.

Extension Consent: The consent for the extension will be shown to participants/caregivers at the beginning of the trial and again at the end of the RCT component. A separate informed consent form and signature page for the extension will be signed for participation in the extension phase of the trial.

Consent for controls providing a stool sample: There will be a separate consent form and signature page for this portion of the study. Adult participants will sign on their own behalf and parents/caregivers will sign on behalf of children. If appropriate based on cognitive age and ability, assent will be obtained from subjects aged 7-17. We will be asking family members of participants in the trial to complete this portion of the study and we will also recruit controls through the Healthy Infants and Children's Clinical Research Program (HICCUP).

### 5) Study Timelines

The study plans to enroll 60 participants over a 3-year period at each site. Approximately 20 patients per year with FXS will be randomized at each site to receive either metformin or placebo for a 4-month period. During the 4-month study period, subjects will attend three visits to the recruiting site: screening/baseline, 2-month, and 4-month visits. In addition, routine phone calls will be made once per week during the first month of the study, with the week 4 phone call being conducted by the study physician, and once at week 12/month 3.

Extension Visit schedule: Informed consent will be obtained either concomitantly to visit 3 of the original schedule of the RCT portion or later if the participant finished the RCT already, but would like to enter the open-label extension. A follow up in-person visit will be done at 1 year of the open-label trial, or before if needed, and another in-person visit will occur at 2 years. Scheduled follow up phone calls will be done weekly for the first month of the extension and then every 4 months. If a participant begins the extension study within 1 year of ending the RCT portion of the study, Visit 3 of the RCT will be considered to be Visit 1 of the extension and the participant would be seen at a 1 year follow up from when they had their Visit 3 of the RCT portion. Those participants previously enrolled in the RCT who have been taking metformin off-label for more than a year can be enrolled in the extension phase. These participants will have a 'first visit' for the extension phase in addition to the previously-completed third visit for the RCT (as that visit occurred more than a year before starting the extension phase). Informed consent will be obtained at this 'first visit'.

# 6) Study Endpoints

The primary outcome measure will be the Expressive Language Sampling (ELS) measure which is conducted at baseline and at the end of treatment, as described in detail in Section 7. The ADOS-2 and Leiter-III will be administered at baseline only for purposes of study population characterization and will not be repeated as outcome measures. All other measures will be secondary outcome measures and are also described in detail in Section 7. Attempts will be made to administer all secondary measures for each participant, to the extent his or her cognitive age and ability allows. Safety endpoints will include safety blood draws and physical exams at each study visits.

For the extension, the primary outcome measure will remain the Expressive language sampling (ELS) measured at the 1 year and 2 year visits. This will provide a connection with the RCT primary outcome. The extension secondary outcome measures will be measured at the 1 year and 2 year visits and will include: Leiter IQ test, Vineland (version 3 for English and version 2 for French), Memory Game (online), NIH Toolbox, CarerQol-Quality of life questionnaires (online), EQ-5D- Health economics questionnaires (online), Pediatric Quality of Life (PedsQL) Parent

Proxy Questionnaire (online), Aberrant Behavior Checklist–Community (ABC-C) (online), Visual Analogue Scale (VAS) (online), Swanson, Nolan and Pelham Questionnaire (SNAP-IV) (online), Clinical Global Impression Scale–Improvement (CGI-I) (online), Anxiety Depression and Mood Scale (ADAMS) (online), Sensory Profile-2 or Sensory Profile Adolescent/Adult, Child Sleep Habits Questionnaire (CSHQ) (online), Automated Self-Administered 24-Hour Dietary Assessment Tool (ASA24), biological biomarkers (blood, stool, and urine), resting EEG and event related potentials (ERPs), and eye tracking.

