Dimensional Change Card Sort Test (Zelazo et al., 2013) – Dimensional Change Card Sort Test is a measure of cognitive flexibility. Two target pictures are presented that vary along two dimensions (i.e., shape and color). Participants are asked to match a series of bivalent test pictures (e.g., yellow balls and blue trucks) to the target pictures, first according to one dimension (e.g., color) and then, after a number of trials, according to the other dimension (e.g., shape). "Switch" trials are also employed, in which the participant must change the dimension being matched. For example, after four trials matching on shape, the participant is asked to match on color in the next trial and then switch back to matching by shape. Scoring is based on a combination of accuracy and reaction time (computed score, ranging from 0–10), and the test duration is about 4 minutes. Dimensional Change Card Sort Test demonstrates good test-retest reliability (ICC=0.74) and correlates well with FSIQ (r=0.66) in children and adolescents with ID, including FXS (Hessl et al., 2016). Aside from having general EF deficits, individuals with FXS have notable impairments in cognitive flexibility and show perseveration in response patterns (Abbeduto and Hagerman, 1997; Hooper et al., 2008).

List Sorting Working Memory Test (Zelazo et al., 2013) – This test requires immediate recall and sequencing of different visually and orally presented stimuli. Pictures of different foods and animals are displayed with accompanying audio recording and written text (e.g., "elephant"), and the participant is asked to state the items in size order from smallest to largest, first within a single dimension (either animals or foods, called 1-

List) and then on 2 dimensions (foods, then animals, called 2-List). The raw score is the number of items recalled and sequenced correctly, and the test takes approximately 7 minutes to administer.

Pattern Comparison Processing Speed Test (Zelazo et al., 2013) – This test measures speed of processing by asking participants to discern whether two side-by-side pictures are the same or not the same by touching "yes" or "no" (or a happy or frowning face for lower mental age). Participants' raw score is the number of items correct in a 90-second period. The items are designed to be simple to distinguish. The test takes approximately 3 minutes to administer.

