The analysis of treatment efficacy will be based on the analysis of covariance (ANCOVA) with outcomes (receptive and expression language at 4-month follow-up with corresponding baseline measure as a covariate). The chosen endpoint at 4-month, based on preliminary data, provides a reasonable treatment time period to assess changes in the response. The proposed method adjusts for potential baseline differences between treatment arms despite randomization, if any. The sample size/power for the ANCOVA is based on sample size needed for a t-test by a variance inflation factor 1-2 where there is the correlation between baseline and follow-up measures. From our preliminary data, the receptive and expressive scores have ranges from approximately 0.2 to 0.5. Thus, we predict power for the t-test and power for the ANCOVA will be higher depending on this factor. We estimate clinically relevant effects sizes, based on our preliminary data, at follow-up visit as follows (metformin/placebo): receptive language score mean 18.1/23.8, SD=7.0; expressive language score mean 13.6/20.7, SD=8.4. For these effect sizes of the 2 primary measures, the ANCOVA will have power of at least 80% (or have between 0.2-0.5) at level alpha=0.016 with the proposed total sample size n = 60 for each group (placebo and treatment).

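### Prespecifying age and baseline Leiter-III as ANCOVA covariates, beside the baseline outcome score, would buy some precision at almost no cost

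*Combined protocol and SAP*

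**What the plan says.** Section 8 (analysis paragraph under Confidentiality) bases efficacy on an ANCOVA of "receptive and expression language at 4-month follow-up with corresponding baseline measure as a covariate". No other covariate is named there. The same paragraph reports that "the receptive and expressive scores have ranges from approximately 0.2 to 0.5". In context this reads as the correlation between baseline and follow-up, because it feeds the variance factor applied to the t-test sample size.

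Section 6 says of the main study: "The ADOS-2 and Leiter-III will be administered at baseline only for purposes of study population characterization", and adds that these tests are not repeated as outcomes. The Leiter-III also sets eligibility. Section 4, inclusion item 10, requires: "Overall age equivalent is not higher than 13 and IQ is not higher than 85, as assessed at Screening on the Leiter-III". Item 2 admits males and any "non-pregnant, non-lactating female age 6 through 35 years, inclusive".

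Section 7 places randomisation after the baseline studies, so age and Leiter-III are available for every randomised participant. Section 7 also describes an adjustment of the Number of Different Words (NDW) for talkativeness. Section 18 stratifies randomisation by sex, not by age or cognitive level.

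**The concern.** The outcome is language performance in a sample that runs from six-year-olds to adults of 35, with non-verbal ability anywhere up to the eligibility ceiling. Section 7 describes no age norming of NDW. Age and cognitive level are natural prognostic variables, and both are already collected.

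On the plan's own correlation of 0.2 to 0.5, the single covariate explains 0.2² = 4% to 0.5² = 25% of follow-up variance and leaves 75% to 96% unexplained. If age or Leiter-III explains part of that remainder, omitting them makes the confidence interval for metformin versus placebo wider than the collected data require. Precision is all that is at stake; randomisation keeps the baseline-adjusted comparison valid.

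**Working it through.** **1. The plan's power statement.** Inputs from Section 8: receptive means 18.1 and 23.8, SD 7.0; expressive means 13.6 and 20.7, SD 8.4; alpha 0.016 (two-sided assumed); 60 per group. Standardised effects are 5.7/7.0 = 0.814 and 7.1/8.4 = 0.845. The residual SD is taken as SD × √(1 − ρ²), and power uses the normal approximation.

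Worked case, receptive, ρ = 0.2: residual SD = 7.0 × √0.96 = 6.86; SE = 6.86 × √(2/60) = 1.252; 5.7/1.252 − 2.409 = 2.14; power 98.4%.

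| Per group | Receptive, ρ = 0.2 / 0.5 | Expressive, ρ = 0.2 / 0.5 |
|---|---|---|
| 60 | 98.4% / 99.7% | 99.0% / 99.8% |
| 30 | 79.1% / 89.1% | 82.4% / 91.5% |

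The claim of at least 80% holds at 60 per group. The 30-per-group row is shown because the sentence also calls 60 the total.

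**2. Gain from one added predictor.** Let r be the baseline/follow-up correlation and k the predictor's correlation with each of them (taken as equal). Then

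R² = (r² + k² − 2rk²)/(1 − k²), and SE ratio = √[(1 − R²)/(1 − r²)].

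The documents give no value of k for this outcome. The range 0.3 to 0.66 is assumed. Its top is borrowed from the Dimensional Change Card Sort Test in Section 7, which "correlates well with FSIQ (r=0.66) in children and adolescents with ID, including FXS". That is a different outcome and a different IQ measure.

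| r | k | R² | SE reduction |
|---|---|---|---|
| 0.5 | 0.3 | 0.275 | 1.7% |
| 0.5 | 0.5 | 0.333 | 5.7% |
| 0.5 | 0.66 | 0.443 | 13.8% |
| 0.8 | 0.3 | 0.644 | 0.6% |
| 0.8 | 0.66 | 0.671 | 4.4% |
| 0.2 | 0.3 | 0.103 | 3.4% |
| 0.2 | 0.447 | 0.200 | 8.7% |

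**3. Why the r = 0.2 rows stop at k = 0.447.** The partial correlation of baseline with follow-up, given the predictor, is (r − k²)/(1 − k²). At r = 0.2 it is (0.2 − 0.25)/0.75 = −0.07 for k = 0.5, and (0.2 − 0.4356)/0.5644 = −0.42 for k = 0.66. Those inputs would mean that, at equal cognitive level, better baseline language predicts worse follow-up language. The value stays non-negative only for k ≤ √0.2 = 0.447.

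**4. Effect on power.** Let p be the share of residual variance removed.

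- 60 per group, receptive, ρ = 0.2: 98.4% rises to 99.2% at p = 0.10. Even p = 0.30 adds only about 1.5 points.
- 30 per group, receptive, ρ = 0.2: 79.1% rises to 83.7% at p = 0.10.
- True effect 0.5 SD (an assumption), 60 per group: 65.0% rises to 70.4% at ρ = 0.2, p = 0.10. At ρ = 0.5, 77.4% rises to 82.2% (p = 0.10) or 87.0% (p = 0.20).

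**5. Cost.** With 120 participants, two arms and one covariate, 117 residual degrees of freedom remain. As a rough guide, useless covariates would raise the SE by √(117/115) − 1 = 0.9% for two terms or √(117/114) − 1 = 1.3% for three.

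**The case against.** Baseline-adjusted ANCOVA is a standard, valid analysis, and further covariates are an option. That stands, and it is why the point is minor.

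A reader might infer that all variance due to age and cognitive level sits in the error term. It does not: baseline language already absorbs the part it shares with them, and only the remainder is left.

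A reader might also take Section 6 as barring the Leiter-III from the model. Its sentence contrasts description with repeated outcome testing and does not prohibit covariate use. The test also sets eligibility, and the caps on IQ and age equivalent narrow its range and so its predictive value.

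The strongest objection concerns size. The 0.2 to 0.5 correlation is attached to receptive and expressive scores for which the lower mean is the metformin one. The primary outcome in Sections 6 and 7 is NDW, where lower would be worse, so these may be different measures. Section 7 rates the retest reliability of NDW very highly without giving a figure. If that means a correlation near 0.8, the gain is 0.6% to 4.4%, and with weak predictors the cost of two or three terms could cancel it. This also stands. It limits the expected benefit but does not remove the case for deciding the covariates in advance.

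**Conclusion.** The point holds as a modest gain in efficiency. The stated ANCOVA omits two plausible prognostic variables that are known before randomisation, and whatever they explain beyond baseline language stays in the residual.

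Under the assumed range for a single predictor, the SE reduction is about 1.7% to 13.8% at a baseline correlation of 0.5 and 0.6% to 4.4% at 0.8. At 0.2 it is 3.4% for k = 0.3, with a ceiling of about 8.7%. These figures rest on assumed correlations; there is no document figure for age at all, and the joint gain from age plus Leiter-III was not calculated.

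The documents do not support reading this as bias, as a type I error problem, or as a trial underpowered for want of covariates: at the stated effects and 60 per group, power is about 98% or more. The gain matters more if the true effect is smaller or if only 30 per group are enrolled.

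**What to change.** In the Section 8 analysis paragraph, prespecify before unblinding that the ANCOVA includes age and baseline Leiter-III alongside the baseline outcome score. Use the Leiter-III age-equivalent or raw score to limit floor effects, a problem Section 7 itself raises for standardised intelligence tests. State whether age enters linearly or with one non-linear term. Keep the baseline-only model as a sensitivity analysis. In Section 6, add that the Leiter-III also serves as a covariate.

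The cost is a few lines of text and 2 to 3 of about 117 degrees of freedom, with no new data. The choice should be fixed before unblinding, because covariates picked afterwards invite selection.
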